- migraine prophylactic therapy without immediate discontinuation of the overused medication.

7. Study Design

This is a prospective, parallel group, simple randomized trial during which patients will be randomized 1:1 to one of two treatment strategies:

- migraine prophylactic therapy with immediate discontinuation of the overused medication
- migraine prophylactic therapy without early discontinuation of the overused medication.

8. Subject Eligibility

Inclusion Criteria

- Adults, at least 21 years of age
- Chronic Migraine diagnosed according to ICHD3beta criteria
- Medication Overuse diagnosed according to ICHD3beta criteria
- Willingness to be randomized to either of the two treatment arms
- Willingness to maintain a headache diary
- Plan for follow-up care with the clinician
- No changes to migraine prophylactic therapy within the 4 weeks prior to randomization

Exclusion Criteria

- Younger than 21 years of age
- Headache diagnoses other than chronic migraine with medication overuse; episodic tensiontype headache on 3 or fewer days per month is allowed
- Not willing to be randomized to either of the treatment arms
- Not willing to maintain a daily headache diary
- Not planning on follow-up care with the clinician
- In the opinion of the clinician, randomization to either treatment arm would be considered unsafe (Ex pregnancy, immediate discontinuation).
- Prisoners
- Diminished decision-making capacity which in the investigator's opinion would interfere
 with the person's ability to provide informed consent and complete study procedures.

ICHD3beta Diagnostic Criteria for Chronic Migraine

Chronic Migraine Diagnostic Criteria

- A. Headache (tension-type-like and/or migraine-like) on ≥15 days/month for >3 months and fulfilling criteria B and C
- B. Occurring in a patient who has had ≥5 attacks of migraine with or without aura
- C. On ≥8 days/month for >3 months, fulfilling any of the following:
 - a) migraine without aura diagnostic criteria
 - b) migraine with aura diagnostic criteria
 - c) believed by the patient to be migraine at onset and relieved by a triptan or ergot derivative
- D. Not better accounted for by another headache diagnosis

ICHD3beta Diagnostic Criteria for Medication Overuse

Medication Overuse Diagnostic Criteria

A. Regular intake of ergotamine, triptans, opioids, combination analgesics, or a combination of drugs from different classes on ≥10 days per month for >3 months

01

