
"bridging therapy", and will be immediate. Several studies have shown that outpatient discontinuation is effective and is similarly effective when compared to inpatient strategies for discontinuation. [Creac'h 2011] [Munksgaard 2012] [Rossi 2006] Since several studies have demonstrated a lack of benefit from prescribing transitional or "bridging" therapy, such as steroid tapers or occipital nerve blocks, during the discontinuation period, this protocol will not call for patients to be prescribed transitional therapy. [Dilli 2014] [Halker 2013] [Rabe 2013] [Boe 2007] If a patient requires inpatient detoxification (according to the opinion of the treating clinician) due to excessive use of opioids or butalbital-containing analgesics or if immediate discontinuation of the overused medication is not possible due to safety concerns, that potential participant will be excluded from this study. Otherwise, there will not be eligibility restrictions based on the medications that patients overuse.

Discontinuing the Overused Abortive Medication(s) (RQ-2) (RQ-5)

- Discontinuation is to be achieved in the outpatient setting
- No "bridging therapy" is to be prescribed (e.g. corticosteroids, extracranial nerve injections, daily NSAID use, ambulatory infusion therapy)
- The overused abortive medication(s) is/are to be immediately stopped and restricted use (\leq 2 days per week) of an alternative abortive medication will be recommended

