e. Symptomatic Therapy for Patients Randomized to Discontinuation of the Overused Medication: Clinicians will also be provided with instructions regarding the methods of prescribing alternative abortive medications to patients randomized to prophylactic therapy plus discontinuation of medication overuse. The specific medications from which the clinician can choose are detailed below and are based upon the American Headache Society, American Academy of Neurology, and Canadian Headache Society guidelines for abortive therapy of migraine. (Marmura 2015; Silberstein 2000; Worthington 2013) Although these patients will not continue to overuse abortive medications, they will be allowed to treat their most severe migraines within the limits imposed by this study protocol. We have chosen not to recommend complete cessation of all abortive therapies since that strategy would not be patient-centered, would likely result in many patients seeking emergency therapy (e.g. emergency department visits), and would increase the rates of patient non-adherence and study dropout.

- Avoid use of medications from the same class as the overused medication
- Up to 2 days per week:
 - o Metoclopramide 10-20 mg or
 - o Prochlorperazine 10 mg or 25 mg suppository
 - Odansetron 4mg-8mg (For patients with a history of extrapyramidal side effects or sensitivity to dopamine antagonists, or a personal or family history of a bradykinetic or hyperkinetic movement disorder)
- Up to 2 days per week
 - Triptans
 - almotriptan 12.5 mg
 - eletriptan 40 mg
 - frovatriptan 2.5 mg
 - naratriptan 2.5 mg

- rizatriptan 5-10 mg
- sumatriptan
 - oral 50-100 mg
 - nasal spray 10-20 mg
 - patch 6.5 mg
 - subcutaneous 4-6 mg
- zolmitriptan
 - oral 2.5-5 mg
 - nasal spray 5 mg

OR

- o Dihydroergotamine
 - nasal spray 2 mg
 - intravenous, intramuscular, or subcutaneous 1 mg

OR

Ketorolac intramuscular 30 mg

OR

o Diphenhydramine intramuscular 25-50 mg

OR

- o Non-steroidal anti-inflammatory drugs
 - aspirin 500 mg
 - diclofenac 50-100 mg
 - ibuprofen 400-600 mg
 - naproxen 400-550 mg

OR

- Combination analgesics
 - acetaminophen/aspirin/caffeine 500/500/130 mg
 - sumatriptan/naproxen 85/500 mg

OR

o Ergotamine tartrate 2 mg

OR

- o Gepants
 - rimegepant 75 mg
 - ubrogepant 50-100 mg

OR

o Lasmiditan 50-200 mg

f. Symptomatic Therapy for Patients Randomized to Prophylactic Therapy Without Discontinuation:

- New abortive medications are not to be recommended

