- Calendar period (before or after initiation of virtual visits)

11. Sample Size and Data Analyses Plans

a. Sample Size

The sample size was calculated based upon showing non-inferiority of prophylactic therapy alone compared to prophylactic therapy with early discontinuation of overused medication. An effective sample of 288 per group (80% of 360) has 80% power (two-sided α .05) to determine that the mean difference is less than 1.5 moderate to severe headache days per four weeks, assuming a population difference of 0.0 moderate to severe headache days per four weeks (pooled SD 6.4 from Silberstein 2013).

b. Data Analyses Plans

Patients will be included in the primary analysis on the basis of intention-to-treat. The frequency of moderate to severe headache days during the 9-12 week post-randomization period will be compared among the two treatment groups by using a two-sample t test. The primary test will be a test of noninferiority. The noninferiority margin will be defined as a mean difference of 1.5 moderate to severe headache day per four weeks. A second primary measure will be assessed by using a fixed sequence gatekeeper strategy. If noninferiority is demonstrated for the frequency of moderate to severe headache days during the 9-12 week period, then a test of superiority will be performed for the frequency of moderate to severe headache days during the first 2 weeks postrandomization. Missing values will be handled by multiple imputation. Pattern mixture modeling will be used if the pattern of missing data differs between groups. In addition, baseline characteristics for subjects with missing primary outcome data will be compared to those without missing data. An interim analysis will be performed using data from 12 weeks after the 360th subject has been randomized. Interim analyses will be performed by using the alpha spending function method with a Haybittle-Peto boundary function. Results will be considered statistically significant if the nominal significance level is less than 0.001 at the interim analyses, or less than 0.049 at the final analysis. Per-protocol analyses will be performed in addition to the intention-to-treat analyses because the primary hypothesis is based on noninferiority. The intention-to-treat and per-protocol analyses would both have to demonstrate non-inferiority to consider the trial positive.

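### The per-protocol analysis can overturn a positive result, but its population is undefined and no method is given that would limit the effect of unequal exclusions between arms

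*Combined protocol and SAP*

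**What the plan says.** Section 11b analyses the primary outcome (moderate to severe headache days per four weeks, weeks 9-12) by intention-to-treat with a two-sample t test. It sets the margin: "The noninferiority margin will be defined as a mean difference of 1.5 moderate to severe headache day per four weeks". It then adds: "Per-protocol analyses will be performed in addition to the intention-to-treat analyses", and counts the trial as positive only if both analyses show noninferiority. It lists no excluding deviations and gives no adherence threshold, assessment window or separate method for the per-protocol comparison. Treatment adherence is a secondary outcome in Section 10b, also without a definition.

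The arm-specific requirements are unequal. In the discontinuation arm (Section 9d), "The overused abortive medication(s) is/are to be immediately stopped and restricted use" of an alternative, on at most 2 days per week, is recommended. In the other arm (Section 9f), "New abortive medications are not to be recommended"; there is no limit on use, and clinicians are to tell patients that use should fall as headaches improve.

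Other requirements apply to both arms: eligibility (Section 8), a change in prophylaxis and no barred adjunctive techniques for 12 weeks (Section 9c), the diary (Section 9g), and a 12-week visit with the assigned strategy kept until then (Section 9, Twelve Week Follow-Up Visit).

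**The concern.** A required analysis needs a population that is fixed in advance, and this one has none. Two things follow.

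First, the choice of exclusions could be made after outcomes are known. The plan describes no blinding, and the treating clinician works within the assigned strategy.

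Second, if adherence is judged by abortive use, only the discontinuation arm has a demanding rule for patients to break. Patients enter with headache on at least 15 days per month, while the restriction allows about 2 × 4 = 8 treatment days per four weeks. Patients with more headache are plausibly the ones who exceed it. Removing them leaves a favourable selection of the discontinuation arm to be compared with a nearly complete continuation arm. The background section before Section 6 reports the argument that letting patients keep their abortive drugs would probably improve adherence, so unequal adherence is foreseeable from the protocol itself.

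At stake is a false veto of the primary conclusion. The superiority test for the first 2 weeks and the confirmatory analysis by type of overused drug also depend on noninferiority having been shown.

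**Working it through.** **Inputs from the plan.** Section 11a: "An effective sample of 288 per group (80% of 360) has 80% power (two-sided α .05"), SD 6.4, "assuming a population difference of 0.0 moderate to severe headache days per four weeks". Section 11b: margin 1.5; significance "less than 0.049 at the final analysis" (one-sided 0.0245, z = 1.969). Section 7: "patients will be randomized 1:1 to one of two treatment strategies".

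**Reproducing the plan's figure.** n per arm = 2 × 6.4² × (1.960 + 0.842)² / 1.5² = 286, or 288 at the final level of 0.049. With 288 per arm, SE = 6.4 × √(2/288) = 0.533. Power = Φ(1.5/0.533 − 1.960) = 80.3%, or 80.1% at 0.049. Also 288/0.80 = 360. The sample size is sound, but it covers one analysis at the full effective n and makes no allowance for per-protocol exclusions.

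**Effect of one-sided exclusion.** These are assumed values, since the documents give none. Let a share q be removed from the discontinuation arm only, and let those removed average D more days than those kept. The true intention-to-treat difference is 0.

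- Shift against noninferiority = q × D
- SE = 6.4 × √(1/288 + 1/[288(1 − q)])
- Power = Φ((1.5 − qD)/SE − 1.969)

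For q = 20%, SE = 6.4 × √(1/288 + 1/230.4) = 0.566:

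- D = 0: Φ(1.5/0.566 − 1.969) = 75%
- D = 3: shift 0.6, Φ(0.9/0.566 − 1.969) = 35%

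The table uses the noncentral t distribution for per-protocol power. The last column is a simulation of 20,000 trials, with overall SD held at 6.4, of both analyses passing.

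| q | D (days) | Shift (days) | Per-protocol power | Both pass |
|---|---|---|---|---|
| 0 | – | 0 | 80% | 80% |
| 10% | 0 | 0 | 78% | not run |
| 10% | 2 | 0.2 | 66% | not run |
| 10% | 3 | 0.3 | 59% | 58% |
| 20% | 0 | 0 | 75% | 74% |
| 20% | 2 | 0.4 | 49% | 50% |
| 20% | 3 | 0.6 | 35% | 36% |
| 30% | 0 | 0 | 72% | 70% |
| 30% | 2 | 0.6 | 33% | 34% |
| 30% | 3 | 0.9 | 17% | 18% |

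The D = 0 rows separate two effects. At q = 20%, the fall from 80% to 75% is only smaller n; the fall from 75% to 35% comes from the shift.

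**Exclusions in both arms.** With the same D in each arm, the net shift is (difference in shares) × D. With 20% from each arm and D = 3, the shift is 0 and both analyses pass about 70% of the time. With 30% from the discontinuation arm and 10% from the other, the shift is 0.2 × 3 = 0.6 and both pass about 33% of the time.

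**Opposite direction and false positives.** If those excluded average 3 fewer days (q = 30%), per-protocol power is 98% and both pass about 80% of the time. At a true difference of 1.5 in that setting, per-protocol alone would pass 34% of the time, but both pass only 2.5%, because intention-to-treat holds the error rate.

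**The case against.** A reader might infer that the plan's rule removes patients almost only from the discontinuation arm and so produces a biased deciding test. The documents do not support that, for four reasons.

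- **No rule is stated.** What exists is a missing definition and a foreseeable risk. The use of the t test for the per-protocol set is also an inference: Section 11b ties it to the primary comparison and names no other method.
- **Shared requirements can remove patients from either arm.** Eligibility errors, prophylaxis not started, barred techniques or a missed 12-week visit could arise in both, and the continuation arm has its own provision on new abortives. One-sided exclusion follows only from a rule based on abortive use. This stands, although shared criteria do not cancel the unequal one.
- **The direction is assumed.** The background section reports opposing expert views on whether overuse drives headache, and no figure shows that patients who fail to stop have more headache days. The link between headache and abortive use makes that direction plausible, not certain.
- **A per-protocol shift is not all bias.** If stopping helps, patients who do not stop dilute the intention-to-treat contrast, and part of the shift is the real difference that a per-protocol analysis is meant to reveal. The calculation treats the whole of qD as selection and cannot separate the two.

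None of this removes the need to fix the set and its analysis in advance.

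**Conclusion.** The concern holds as a risk to a deciding analysis. The text establishes that the per-protocol result is required for a positive trial, that its population is undefined, and that the abortive-use demands fall mainly on one arm. It does not establish which patients would be excluded or how they differ from the rest.

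Under the assumed one-sided exclusion of 20%, per-protocol power is about 75% without selection and about 35% if those excluded average 3 more days, against about 80% with no exclusions. In the second case the shift of 0.6 days is 0.6/1.5 = 40% of the margin. Every exclusion share and day difference here is an assumption.

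A reader might also fear a false claim of noninferiority. The both-must-pass rule prevents that, so the harm is a possible false veto and room for choices made after the data are seen.

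**What to change.** Amend Section 11b before any arm-level outcome data are seen:

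1. **Define the set.** List criteria common to both arms (eligible, baseline prophylactic change started, no barred technique) and one diary-based adherence rule for each arm, drawn only from requirements already in Section 9. State the assessment window and how days without a diary entry count. A window that overlaps weeks 9-12 measures adherence and outcome on the same days.
2. **Do not exclude for missing weeks 9-12 diary data.** Leave these to the multiple imputation already planned; a completeness criterion would add exclusion that may depend on outcome.
3. **Adjust the per-protocol estimate** for baseline data already on the case report forms: moderate to severe headache days, frequency and class of overused medication, GAD-7 and PHQ-9. Use inverse-probability weighting as a sensitivity analysis.
4. **Report exclusions by arm and reason.**

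The cost is SAP wording and slightly more analysis, with no new data collection. Baseline adjustment removes only the selection explained by baseline variables. It cannot remove selection driven by headache after randomization, and the SAP should state this as a limitation.

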B. Regular intake of simple analgesics (e.g. acetaminophen, NSAIDs) on \geq 15 days per month for >3 months

9. Study Procedures

Consecutive patients presenting to the investigator's clinic, whether in-person or via telehealth methods, who meet inclusion/exclusion criteria should be offered enrollment. As a pragmatic study, potential participants will not be excluded based upon measures of clinical severity or based upon preconceived notions of their likelihood to respond to the study interventions. Chronic migraine patients with medication overuse will be identified just as they are in daily clinical practice – according to the patient's report of headache frequency, headache symptoms, acute medications used and their frequency of use. Patients with excessive use of opioids and butalbital containing medications such that immediate discontinuation, in the opinion of the investigator, will pose an unacceptable risk of withdrawal syndrome and a serious risk to patient safety will be excluded (this is expected to be a very small proportion of patients who have chronic migraine with medication overuse). We anticipate that about 90% of patients who are screened for this study will be eligible and 40% of eligible patients will agree to participate in this study. Thus, in order to meet enrollment targets we estimate that headache specialty centers will have to screen approximately 5-6 patients per month, while general neurology and primary care clinics will have to screen about 2 patients per month. In total, each headache specialty clinic is expected to enroll 24 patients per year, while general neurology and primary care clinics are expected to enroll 8 patients per year.

Recruitment Plan

	# patients screened each month	# patients enrolled each year			
Headache Specialty Clinic	6	24			
General Neurology Clinic	2	8			
Primary Care Clinic	2	8			

Study Visits

Each subject **must** have a research visit at baseline/randomization and at 12 weeks post-randomization. These research visits can occur in-person or using IRB-approved telehealth methods, such as, but not limited to telephone, video, e-mail, and regular mail. Other follow-up visits will occur according to the clinician's usual follow-up patterns (these are clinical visits, not study specified visits).

Baseline/Randomization Visit

a. Case Report Forms: The following case report forms and questionnaires are to be completed at the baseline visit:

- Inclusion/Exclusion Criteria

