- Clinicians will be instructed to discuss the following with the patient: 1) prophylactic medication is being initiated or current prophylactic medication(s) is/are being adjusted; and 2) as a result, it is expected that migraine frequency will reduce and thus abortive medications will be required less frequently.

g. Headache Diary: Patients will maintain a daily headache diary during the following post-randomization weeks:

- 1-12 (days 1-84)
- 21-24 (days 141-168)
- 45-48 (days 309-336)

At the baseline visit, patients will need to receive instructions on the use of the electronic/internet based headache diary that is within the Medidata Rave system. Patients may choose to use either the online or app version of the diary (or a combination of both). Sign-in information needs to be obtained. A paper headache diary is also to be given to patients along with instructions for use.

This migraine and medication diary will require participants to record whether or not they had a headache on a given day, the maximum severity of headache pain during that day, whether the headache caused no, mild, moderate or severe functional impairment, whether or not they took migraine abortive medications that day (and which medication), whether or not they took migraine prophylactic medication that day, and any changes to their treatment regimen.

Twelve Week Follow-Up Visit

All subjects are to be seen for follow-up at 12 weeks post-randomization (+/- 1 week). This 12-week visit can be accomplished in-person (i.e. in the office) or using IRB-approved telehealth methods, such as, but not limited to telephone, video, e-mail, regular mail, and by completing internet-based questionnaires.

Subjects are to remain in the treatment group to which they were randomized through this 12-week visit. Subjects will remain in this study through week 48, but treatment recommendations starting with week 13 will be according to the clinician's usual clinical practice.

h. Case Report Forms: The following case report forms and questionnaires are to be completed at the 12-week visit:

- Follow-up Visit Headache Characteristics
- Medication Use
- Headache Impact Test 6 (HIT-6)
- PROMIS Pain Interference questionnaire
- Generalized Anxiety Disorder 7 (GAD-7)
- Patient Health Questionnaire 9 (PHQ-9)
- EuroQol 5D (EQ-5D-3L)
- Change in Migraine Therapy
- Migraine Functional Impact Questionnaire (MFIQ)

Other Follow-Up Visits and Telephone Contacts

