The timing of these follow-up visits is left to the discretion of the clinician. However, consistent with good clinical care of patients who have chronic migraine with medication overuse, follow-up visits

are expected to occur approximately each 2-3 months. These visits can be accomplished in-person (i.e. in the office) or using IRB-approved telehealth methods, such as, but not limited to telephone, video, e-mail, regular mail, and by completing internet-based questionnaires.

i. Case Report Forms: At each follow-up visit, the following case report forms are to be completed:

- Follow-up Visit Headache Characteristics
- Medication Use
- Headache Impact Test 6 (HIT-6)
- PROMIS Pain Interference questionnaire
- Generalized Anxiety Disorder 7 (GAD-7)
- Patient Health Questionnaire 9 (PHQ-9)
- EuroQol 5D (EQ-5D-3L)
- Change in Migraine Therapy
- Migraine Functional Impact Questionnaire (MFIQ)

j. Headache Diary Adherence Monitoring:

Monitoring patient adherence to diary keeping and sending reminders to each participant will be necessary for improving adherence to daily diary keeping. The research team should monitor each patient's completion of the headache diary on a weekly basis. If non-adherence is noted, the study team should contact the patient via telephone, e-mail, text messages, and/or regular mail. In these communications, participants should be reminded to keep their daily headache diary and provided with further instructions if the participant is having any difficulty with the diary. No clinical recommendations should be made during these research communications. In addition, telephone calls, e-mails, text messages, or regular mail will be necessary at the beginning of the 21-24 week period and 45-48 week period to remind the patient to once again start maintaining the headache diary.

- 1-4 weeks post randomization
 - Day 1 after the baseline visit
 - Day 7-9 after the baseline visit
 - o Day 14-16 after the baseline visit
 - o Day 21-23 after the baseline visit
- 5-8 weeks post randomization
 - o Day 28-30 after the baseline visit
 - o Day 35-37 after the baseline visit
 - o Day 42-44 after the baseline visit
 - o Day 49-51 after the baseline visit
- 9-12 weeks post randomization
 - o Day 56-58 after the baseline visit
 - o Day 62-64 after the baseline visit

- o Day 69-71 after the baseline visit
- o Day 76-78 after the baseline visit
- 21-24 weeks post randomization
 - o Day 139-141 after the baseline visit

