 - o Day 146-148 after the baseline visit
 - o Day 153-155 after the baseline visit
 - o Day 160-162 after the baseline visit
- 45-48 weeks post randomization:
 - o Day 307-309 after the baseline visit
 - o Day 314-326 after the baseline visit
 - o Day 321-333 after the baseline visit
 - o Day 328-340 after the baseline visit

k. Changes in Therapy: Changes in the subject's migraine treatment that might occur outside of the follow-up visits (e.g. via a telephone call with the patient) should be documented in the "Medications and Treatments" case report form within Medidata Rave. **10. Study Outcomes**

- **a. Primary Outcome**: The primary outcome measure for this study will be frequency of moderate to severe headache days (i.e. days on which a headache lasts for at least 2 hours and at any time peaks at moderate or severe intensity) per 4 weeks measured during 9-12 weeks postrandomization. If non-inferiority is demonstrated for the primary outcome, then a test of superiority will be performed for the frequency of moderate to severe headache days during the first 2 weeks post-randomization.
- b. Secondary Outcomes frequency of headaches associated with moderate to severe functional impairment, frequency of days taking abortive medications, headache frequency, treatment adherence rates, and rates of subject dropout. (RQ-2) (RQ-6) (PC-3) In addition, relapse rates (i.e. the proportion of subjects who stopped overusing the abortive medication but then returned to the overuse pattern) will be measured using the 21-24 week and 45-48 week data.
 - Frequency of headaches associated with moderate to severe functional impairment
 - Frequency of days taking symptomatic medications
 - Headache Frequency
 - Treatment Adherence Rates
 - Subject Study Dropout Rates
 - Relapse Rates (i.e. the proportion of subjects who stopped overusing the abortive medication but then returned to the overuse pattern)
 - Quality of Life
 - Disability

c. Heterogeneity of Treatment Effects Analyses

- Class of overused medication
- Baseline frequency of taking the overused medication
- Duration of medication overuse

- Years with migraine
- Years with chronic migraine
- Type of provider managing the patient (i.e. headache specialist, general neurologist, primary care physician)
- Frequency of follow-up visits
- Class of prophylactic therapy(s) used
- Baseline headache frequency
- Baseline anxiety and depression scores
- Patient age
- Patient sex
- Type of visit (in person vs. virtual)

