A confirmatory heterogeneity of treatment effect analysis for type of overused medication will be performed if the primary analysis demonstrates noninferiority. (HT-3) Patients will be classified into whether or not the overused medication was an opioid or barbiturate vs. another abortive medication. The frequency of moderate to severe headache days during the 9-12 week period will be compared among the two treatment groups by using a general linear model with terms for group, overused medication category (opioid or barbiturate versus other), and group by category interaction. Descriptive heterogeneity of treatment effect analyses will be performed for duration of overuse, baseline headache frequency, number of years with migraine, number of years with chronic migraine, the type of provider managing the patient (e.g. headache specialist vs. neurologist vs. primary care provider), patient sex, patient age, baseline anxiety and depression scores, the class of prophylactic therapy used, the frequency of follow-up visits with the clinician, type of visit, and calendar period. Analyses concerning prophylactic medications will focus on the therapy that was the change in treatment at the baseline visit. For example, if a participant is

taking medication A at baseline and the clinician adds medication B, it is medication B that would be considered the treatment of interest.

12. Potential Risks and Protection of Human Subjects

The study will be conducted according to Good Clinical Practice guidelines, the Declaration of Helsinki, U.S. 21 Code of Federal Regulations for Protection of Human Subjects, and Institutional Review Boards, and pursuant to state and federal HIPAA regulations. Institutional Review Boards for each participating center must provide unconditional approval prior to that centers participation in this study. Documents proving IRB-approvals will be submitted to the Principal Investigators prior to each center's participation. All protocol amendments will require IRB approvals and documents confirming approval of such amendments will be submitted to the Principal Investigators. Each participating center's IRB and the IRB at the principal investigators' center (Mayo Clinic) will be informed of all serious or unexpected adverse events that occur during the study. Adverse events will also be reported to PCORI, if such reporting of adverse events is consistent with PCORI policy.

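### Follow-up visit frequency arises after randomization and has no baseline anchor, so arm differences within visit-frequency subgroups cannot be read as effect modification

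*Combined protocol and SAP*

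**What the plan says.** Section 10c (Heterogeneity of Treatment Effects Analyses) includes "Frequency of follow-up visits". Section 11b repeats the item in its descriptive list: "the class of prophylactic therapy used, the frequency of follow-up visits with the clinician". Neither section gives a counting window or says whether the mandatory 12-week visit counts. Section 11b names the weeks 9-12 outcome for the confirmatory analysis by type of overused medication. It names no outcome for the descriptive analyses.

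Section 9 describes how the visits arise. Baseline and week 12 are required: "All subjects are to be seen for follow-up at 12 weeks post-randomization", with a window of one week either side. All others follow the clinician's customary practice, and the protocol says of them that "these are clinical visits, not study specified visits". Under Other Follow-Up Visits and Telephone Contacts: "The timing of these follow-up visits is left to the discretion of the clinician", and they "are expected to occur approximately each 2-3 months". Participants stay in the study through week 48. The primary outcome in Section 10a is "measured during 9-12 weeks postrandomization".

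For prophylactic therapy, Section 11b ties the analysis to the change made at the baseline visit. Visit frequency has no such rule.

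**The concern.** A subgroup analysis of a randomized trial keeps the protection of randomization when the subgroup variable is fixed before allocation or cannot be affected by it. Realized visit frequency meets neither condition. The clinician who schedules the visits knows the strategy and sees the patient's course. The background section reports the argument that early discontinuation brings a period of worse headache and impairment. If that happens and worse patients are seen more often, the visit count depends on both arm and headache. Patients labelled frequent visitors in one arm are then not the counterparts of those in the other.

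At stake is the reading of a descriptive table. A difference between arms among frequently seen patients could be reported as showing for whom a strategy works, when it partly reflects who came to be seen often. There is also a question of order: visits made after weeks 9-12 cannot modify a weeks 9-12 outcome.

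**Working it through.** **Plan's own figure.** Inputs from Section 11a: margin 1.5 days, SD 6.4, true difference 0, 80% power, two-sided 0.05. n per group = 2 × (1.960 + 0.842)² × 6.4² / 1.5² = 286. At the plan's 288, power is 80.3%. At the final level of 0.049, n is 288. The sample size reproduces and does not depend on this point. The SD and the 288 are used below.

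**Timing.** Section 9g equates weeks 1-12 with days 1-84, so weeks 9-12 are days 57-84. Week 48 ends on day 336. The 12-week visit falls on day 84 ± 7, that is days 77-91: days 77-84 lie inside the outcome period and days 85-91 after it. Usual visits, assuming regular spacing from baseline:

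| Spacing | Visit days through 336 | By day 56 | By day 84 | After day 84 |
|---|---|---|---|---|
| 8 weeks | 56, 112, 168, 224, 280, 336 | 1 | 1 of 6 | 83% |
| 2 months (60.9 days) | 61, 122, 183, 244, 304 | 0 | 1 of 5 | 80% |
| 2.5 months (76.1 days) | 76, 152, 228, 304 | 0 | 1 of 4 | 75% |
| 12 weeks | 84, 168, 252, 336 | 0 | 1 of 4 | 75% |
| 3 months (91.3 days) | 91, 183, 274 | 0 | 0 of 3 | 100% |

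So 75-100% fall after the outcome period. Counting only visits before it (to day 56) gives 0, or 1 at exactly 8 weeks. That leaves little variation, and the count would still be post-randomization.

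**Possible size, by assumption.** The documents give no link between visits and headache days. Suppose there is no true arm difference in anyone, visit propensity and headache days are bivariate normal with correlation r, SD is 6.4, and half of each arm are frequent visitors. Each subgroup mean then departs from its arm mean by ±6.4 × r × 0.798 = ±5.11r.

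- Same r (0.2) in both arms: subgroup arm differences 0, contrast 0.
- r = 0.2 versus 0.25: ±5.11 × 0.05 = ±0.26 days, contrast 0.51.
- r = 0.2 versus 0.3: ±0.51, contrast 1.02.
- r = 0.2 versus 0.4: ±1.02, contrast 2.04.

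The SE of the contrast with 144 per cell (288/2) is 6.4 × √(4/144) = 1.07 days.

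Now keep r equal and let the share of frequent visitors be 45% in one arm and 55% in the other. The standardized mean among frequent visitors is 0.880 versus 0.720, and among the rest −0.720 versus −0.880. Each differs by 0.160, so both subgroup effects shift by 6.4 × r × 0.160 = 0.20, 0.31 and 0.51 days for r = 0.2, 0.3 and 0.5. The contrast is 0. Exact equality needs shares symmetric about one half. At 20% versus 30% with r = 0.2 the shifts are 6.4 × 0.2 × (1.400 − 1.159) = 0.31 and 6.4 × 0.2 × (0.497 − 0.350) = 0.19, a contrast of 0.12.

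A more extreme simulation let early headache burden alone determine visits, with a median split, no arm effect on weeks 9-12, and a correlation between early burden and outcome of 20/(5 × 6.4) = 0.625. Raising early burden by 1, 2 or 3 days in the discontinuation arm gave apparent differences of about −0.5, −1.0 and −1.5 days, about equal in the two subgroups, while the overall difference stayed near 0.

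**The case against.** The strongest reply has four parts.

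- **Customary practice.** Section 9 says the extra visits follow the clinician's customary pattern, so frequency partly reflects practice that predates allocation. This stands as a limit on the bias. But timing is also left to discretion, and the realized count cannot separate habit from response to the patient.

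- **Descriptive label.** Section 11b reserves its confirmatory heterogeneity analysis for type of overused medication, conditional on noninferiority. This stands for error rates. It does not make a post-randomization subgroup comparable across arms.

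- **No false heterogeneity need follow.** A reader might infer that the analysis will show a spurious difference between frequent and infrequent visitors. The documents do not support that. With the same visit-headache link in both arms the contrast is 0 or small. A material contrast needs the link to differ by arm, and no figure suggests that it does. What remains is that the arm difference within each subgroup may be biased.

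- **Conditional timing.** A reader might take it as settled that most of the visits come too late. That holds only for a count through week 48 and a weeks 9-12 outcome. Relapse, for instance, is measured at weeks 21-24 and 45-48, and later visits are not simply too late for it. Section 14 caps compensated visits at six including the two mandatory ones (so up to four others), but a payment cap is not a counting window.

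**Conclusion.** The point holds and is minor. Realized follow-up visit frequency is not a valid effect modifier here, because it is generated after allocation, at clinician discretion, without a baseline anchor. That conclusion needs no assumption about spacing or correlation.

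The 75-100% figure rests on regular visits at the expected spacing, a count through week 48 and a weeks 9-12 outcome. The mandatory visit falls late in the outcome period or after it. The size of any bias is unknown; all the day figures above are illustrations.

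A reader might also infer that the noninferiority conclusion is at risk. It is not: visit frequency does not enter the primary test, sample size, decision rule or intention-to-treat comparison.

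**What to change.** Remove follow-up visit frequency from the lists in Sections 10c and 11b. Report visit counts by arm as a post-randomization outcome with a stated window, for example weeks 1-12 and weeks 13-48, and say whether the mandatory 12-week visit is counted. Provider type stays on the list as the baseline measure of care setting.

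If the sponsor wants a visit-related modifier, use a pre-randomization measure, such as the clinician's planned follow-up interval recorded before allocation.

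The cost is one item deleted from two lists, a sentence defining the window and a table by arm. No new visit data are needed: "At each follow-up visit, the following case report forms are to be completed". The optional planned interval would add one form entry before randomization. The downside is that the subgroup display by realized visit frequency is lost.
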